**e. Pre-treatment adverse events (PTAEs)**

If there are no serious PTAEs or PTAEs that led to withdrawal, the respective protocol-specified tabular summaries will not be produced. The protocol-specified tabular summary of all PTAEs will be produced, regardless.

**f. Exact logistic regression analyses of TEAEs and treatment-emergent serious adverse events (SAEs)**

An exact logistic regression to compare TEAE rates between amlodipine + celecoxib and amlodipine + placebo, with the TEAE (1 = at least one TEAE occurred for the subject; 0 = otherwise) as the dependent variable, and treatment (amlodipine + celecoxib and amlodipine + placebo) as fixed effects, will be added.

An exact logistic regression to compare treatment-emergent SAE rates between amlodipine + celecoxib and amlodipine + placebo, with the treatment-emergent SAE (1 = at least one treatment-emergent SAE occurred for the subject; 0 = otherwise) as the dependent variable, and treatment

(amlodipine + celecoxib and amlodipine + placebo) as fixed effects, will be added, with the caveat that if there are no treatment-emergent SAEs, the tabular summary will not be produced.

**g. Physical examination**

The physical examination summary tabulation will be limited to the comprehensive physical examinations at the Initial Screening Visit and Day 14 and will not include the targeted physical examinations at Days 0, 7 and 28. The targeted physical examination findings will still be provided as a listing as specified in the protocol. A shift table presenting the number and the percentage of subjects in each bivariate category (Initial Screening Visit versus Day 14) with regards to Investigator's interpretation [normal, abnormal not clinically significant (NCS), abnormal clinically significant (CS), not done, and missing] by treatment arm will be done in place of a frequency only table. Due to the limited number of events, the comparisons among treatment arms using Chi-square, binomial, and logistic analyses will not be done since they would not provide meaningful analyses.

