8.1 Adverse Events

8.1.1 Definitions

8.1.1.1 Adverse Event

An AE is defined in the Guideline for Good Clinical Practice E6(R1) (ICH Harmonised Tripartite Guideline, dated June 10, 1996) as follows:

Any untoward medical occurrence in a subject or clinical investigation subject administered a pharmaceutical product and which does not necessarily have a causal relationship with this treatment. An AE can therefore be any unfavourable and unintended sign (including an abnormal laboratory finding), symptom, or disease temporally associated with the use of a medicinal (investigational) product, whether or not related to the medicinal (investigational) product.

Any untoward medical occurrence that initiates or worsens after completion of the initial screening visit procedures and before administration of the first dose of study drugs will be recorded as a PTAE.

Any untoward medical occurrence that initiates or worsens after the first dose of study drugs and within 14 days of the last dose of study drugs will be recorded as a TEAE.

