8.1.5 Monitoring of Adverse Events

Monitoring for PTAEs will begin upon completion of the initial screening visit procedures and will continue through the 9 to 13 days of washout, the final screening visit on Day -1, and the baseline procedures on Day 0 (i.e., prior to the administration of the first dose of study drugs). Any untoward medical occurrence that initiates or worsens after completion of the initial screening visit procedures and before administration of the first dose of study drugs will be recorded as a PTAE.

Monitoring for TEAEs will begin immediately following administration of the first dose of study drugs and will continue throughout the study. Any untoward medical occurrence that initiates or worsens after the first dose of study drugs and within 14 days of the last dose of study drugs will be recorded as a TEAE.

Subjects will be instructed to report all PTAEs and TEAEs experienced during the study, and subjects will be assessed for the occurrence of PTAEs and TEAEs throughout the study. In order to avoid bias in eliciting AEs, subjects will be asked general, non-leading questions such as "How are you feeling?"

All study drug-related TEAEs (adverse reaction or suspected adverse reaction per the definitions in Section 8.1.3) will be followed until resolution or stabilization of the event. This may require additional clinical assessments and laboratory tests.

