8.2 Physical Examination

A comprehensive physical examination will be performed at the initial screening visit and on Day 14. The comprehensive physical examination will include the following organ or body system assessments: skin; head, eyes, ears, nose, and throat; thyroid; lungs; cardiovascular; abdomen (liver, spleen); lymph nodes; and extremities, as well as an abbreviated neurological exam.

A targeted physical examination will be performed at baseline (Day 0) and at the Day 7 and Day 28 visit. This examination will specifically target the cardiovascular system and will include vital signs, plus an examination of the extremities to check for the presence of edema, as well as an examination to document any other evidence of a cardiovascular problem. Any areas of concern from the medical history or noted on the prior physical examination or indicated by subject symptoms or other findings as determined by the Investigator or designee may also be examined.

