### **Oedema events**

An oedema event is any TEAE with a PT of oedema, oedema peripheral, peripheral swelling, swelling, or joint swelling.

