Similar tabular summaries will be produced for each of the following: treatment emergent SAEs, ADRs, oedema events, other PTs of interest, treatment emergent UAEs, TEAEs leading to discontinuation, PTAEs, PTAEs leading to discontinuation, and pre-treatment SAEs. In the case of the latter two, the summaries will not be produced if there are no PTAEs leading to discontinuation or pre-treatment SAEs, respectively. For the ADR summary, if an ADR is reported more than once for a given subject, the worst-case attribution will be presented in the summary table.

A comparison of TEAE rates between the amlodipine + celecoxib and amlodipine + placebo arms will be performed using an exact logistic regression model with the TEAE ("1"=At least one TEAE occurred for the patient; "0"=otherwise) as dependent variable and treatment (amlodipine + celecoxib and amlodipine + placebo) as fixed effects. The probability modeled will be TEAE="1". The number of patients and the number of patients considered in the model will be provided. The exact odds ratio of the fixed effects will be calculated (amlodipine + celecoxib and amlodipine + placebo) with the relative 95% CI and p-value.

The same model will be repeated by considering treatment-emergent SAE (“1”=At least one treatment-emergent SAE occurred for the patient; “0”=otherwise) as dependent variable, with the caveat that if no treatment-emergent SAEs are reported the table will not be produced.

The rates of oedema events between the amlodipine + celecoxib arm and the amlodipine + placebo arm will be compared using an exact logistic regression and reporting the odds ratio. Oedema event (1 = at least one TEAE with PT of oedema, oedema peripheral, peripheral swelling, swelling, or joint swelling occurring for the subject; 0 = otherwise) will be the dependent variable, and treatment (amlodipine + celecoxib and amlodipine + placebo) will be the fixed effects.

The Fisher’s exact test will be run to compare the number of oedema events that occurred while on treatment (Day 0 to Day 14+1) and post-treatment (>Day 14+1) between treatment arms 1 and 2 (amlodipine + celecoxib and amlodipine + placebo).

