### **Comprehensive physical examination**

Each protocol-specified organ or body system for the comprehensive physical examination will be summarized for the Safety population by a shift table presenting the number and the percentage of patients in each bivariate category (Initial Screening Visit versus Day 14) with regards to Investigator’s interpretation (normal, abnormal NCS, abnormal CS, not done, and missing) by treatment group.

The results of targeted physical examination will be only listed.

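### The examiner's oedema checks at Days 0, 7 and 28 are reduced to a listing, so the only oedema variable compared between arms is reported-event terms with no rule for recording examination findings

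*SAP*

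**What the plan says.** **What is examined.** Protocol 8.2 schedules a targeted physical examination at Days 0, 7 and 28 that includes "an examination of the extremities to check for the presence of edema". It is the only procedure in the protocol that names oedema. The comprehensive examination, at the initial screening visit and Day 14, covers the extremities as one body system among several.

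**What the protocol planned.** Protocol 10.4 says the secondary safety assessments, physical examination among them, will be listed and also summarised. It plans chi-square, binomial and logistic comparisons among arms for dichotomous variables.

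**What the SAP does.** SAP 1.3.9g says: "The physical examination summary tabulation will be limited to the comprehensive physical examinations at the Initial Screening Visit and Day 14". SAP 7.9 adds: "The results of targeted physical examination will be only listed", and SAP 6.4 says the same. The between-arm tests are dropped because few events are expected. The comprehensive examination becomes a shift table by arm, Screening against Day 14, graded normal, abnormal not clinically significant or abnormal clinically significant.

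**What is tested for oedema.** SAP 6.4 defines the variable: "An oedema event is any TEAE with a PT of oedema, oedema peripheral, peripheral swelling, swelling, or joint swelling". SAP 7.9 then says: "The rates of oedema events between the amlodipine + celecoxib arm and the amlodipine + placebo arm will be compared using an exact logistic regression". It also plans a Fisher test of on-treatment and post-treatment oedema events. Under Protocol 8.1.5, adverse events are elicited so that "subjects will be asked general, non-leading questions such as" an open enquiry about how the subject feels.

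**The concern.** Oedema carries weight in this trial's rationale. The Protocol background reports it in 15.6% of amlodipine subjects and 8.2% of combination subjects in the prior study, and builds the fluid-retention hypothesis on that difference. SAP 1.1 repeats the finding as indirect evidence of a renal effect that this trial was designed to confirm.

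The protocol provided a direct check, made by blinded site staff at fixed visits in every subject. The SAP takes those checks out of the tables and removes the protocol's planned comparison. What is tested depends on whether oedema was reported and coded as an adverse event. If sites differed in whether they entered an examination finding on the adverse-event form, the tested variable mixes presence of oedema with reporting habit, and no table would show it. SAP 1.5 identifies v4.0 as the post-unblinding version, so dropping a planned summary needs a reason that fits.

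**Working it through.** **1. Where each extremity finding ends up**

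| Visit | Examination | Names oedema? | Treatment status | SAP display | Arm test |
|---|---|---|---|---|---|
| Screening | Comprehensive | No | On prior antihypertensive | Shift table | None |
| Day 0 | Targeted | Yes | Pre-dose, after washout | Listing | None |
| Day 7 | Targeted | Yes | On treatment | Listing | None |
| Day 14 | Comprehensive | No | Morning after last dose | Shift table v Screening | None |
| Day 28 | Targeted | Yes | About two weeks off drug | Listing | None |

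The one on-treatment examination that names oedema (Day 7) is not tabulated. The end-of-treatment examination (Day 14) is tabulated against a visit made before washout, although SAP 6.5 names Day 0 as baseline for the targeted examination. No table uses that baseline.

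**2. Does the stated reason fit?** SAP 1.3.9g drops the tests because events are few. SAP 1.3.9a and 7.9 add exact logistic regression and a Fisher test for oedema adverse events, which are methods suited to few events. The reason therefore does not separate the two data sources. No reason is given for leaving the targeted examinations out of the summary. SAP 1.3.9g describes the listing as what the protocol specified, but Protocol 10.4 specified a summary as well.

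**3. Can examination findings reach the tested variable?** Protocol 8.1.1.1 says: "An AE can therefore be any unfavourable and unintended sign (including an abnormal laboratory finding), symptom, or disease temporally associated". A sign found by the examiner can therefore be a treatment-emergent event. For laboratory results, Protocol 10.4 says clinically significant abnormalities will be reported as adverse events. There is no matching rule for physical-examination findings. Inclusion is possible but not assured.

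**4. How much power is at stake?** The plan states no sample size or power for oedema, so there is no figure to reproduce.

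Inputs:
- Rates of 15.6% and 8.2%, from the Protocol background.
- Two-sided 5% level, from SAP 7.3.
- n per arm: 105 × 3/7 = 45 as planned, or about 105 × 6/13 = 48 under the 6:6:1 allocation reported in SAP 3.2.

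Power is the sum of Bin(i; n, p1) × Bin(j; n, p2) over all tables (i, j) with two-sided Fisher p ≤ 0.05.

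| Scenario | Rates | n = 45 | n = 48 |
|---|---|---|---|
| Adverse-event rates as in prior study | 15.6% v 8.2% | 0.117 | 0.110 |
| Both rates × 1.5 (assumption) | 23.4% v 12.3% | 0.193 | 0.207 |
| Both rates × 2 (assumption) | 31.2% v 16.4% | 0.287 | 0.315 |
| Both rates × 2.5 (assumption) | 39.0% v 20.5% | 0.402 | 0.427 |
| Both rates + 5 points (assumption) | 20.6% v 13.2% | 0.095 | 0.100 |
| Both rates + 20 points (assumption) | 35.6% v 28.2% | 0.081 | 0.081 |

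If examination finds more oedema at the same ratio, power rises. If it finds extra background oedema equally in both arms, power falls. The documents do not say which would happen. For scale, 80% power at 15.6% v 8.2% needs about 300 per arm (normal approximation).

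**The case against.** The case against is substantial, and much of it stands.

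- **A reader might infer that the oedema test rests only on complaints volunteered by subjects.** The documents do not support that. The adverse-event definition includes signs, Protocol 8.1.5 says subjects are assessed as well as asked, and the adverse-event form takes signs or symptoms when there is no diagnosis. What remains is that no text makes the recording consistent.
- **A reader might infer that examined oedema is never set out by arm.** Day 14 extremities are shown by arm. They are not shown as oedema and are not tested.
- **A reader might infer that three post-dose checks are lost, or that the data are discarded.** Day 28 is off drug, Day 14 is tabulated, and the rest are listed. The untabulated on-treatment check is Day 7. The SAP itself expects blood-pressure effects to be smaller at Day 7 (1.3.9h) and orthostatic effects to be greatest at Day 14 (1.3.9i).
- **Fluid retention is addressed elsewhere.** Body weight, with a Day 0 baseline, is the first secondary endpoint and is compared among arms by ANOVA and again by ANCOVA.
- **Oedema is not a listed objective or endpoint.** Safety rests primarily on reported events, and SAP 1.1 can be read as meaning the renal mechanism rather than oedema itself.
- **The change is declared, with a reason for dropping the tests.** Screening is the SAP's stated baseline for the comprehensive examination, which was done only at Screening and Day 14.

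These points limit the size of the problem. They do not explain why the oedema-specific check is left out of the summary that the protocol planned.

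**Conclusion.** The point holds in a limited form. The only examination that names oedema is listed and neither summarised nor compared, contrary to Protocol 10.4. Day 14 extremities appear in an untested table with no oedema category and a pre-washout reference. The tested variable may or may not contain examiner-found oedema. The practical loss is the Day 7 and Day 14 findings relative to Day 0.

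It is tempting to conclude that the examination data would rescue the oedema comparison. They would not, on present evidence: exact power runs from about 8% to 43% across the assumptions tried, against 11 to 12% for reported events, and the direction of change depends on an ascertainment pattern that the documents do not give. The gain is a second, systematically collected view of oedema and a check on how events were recorded. The primary endpoint and the hierarchy of secondary endpoints are unaffected. This is a cheap improvement, worth making because the trial's rationale leans on oedema.

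**What to change.** In SAP 1.3.9g, 6.4 and 7.9:

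1. Tabulate extremity oedema (present/absent) by arm at Days 0, 7 and 14, with Day 28 shown descriptively as an off-treatment visit.
2. Give the arm 1 v arm 2 odds ratio with exact 95% confidence interval for oedema new or worse than Day 0 at Day 7 or Day 14, counting each subject once.
3. Place it beside the adverse-event analysis, labelled supportive and added after unblinding.
4. Report how many subjects with examiner-found oedema also had an oedema adverse event recorded, by arm.

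The cost is one table and one exact model. Protocol 8.2 defines no yes/no field or grade for oedema and the case report form is not part of the documents, so free-text findings may need a coding pass by someone blinded to treatment. Where severity was not recorded, the outcome reduces to oedema newly present since Day 0. Day 14 comes from the comprehensive examination and Days 0 and 7 from the targeted one; a footnote should say so.

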**h. Vital signs**

Descriptive statistics [n, mean, standard deviation (SD), median and range] will be added for the change from baseline at each visit (Days 7, 14, and 28) for each vital sign (clinic visit resting SBP and DBP, pulse rate, respiration rate, and oral body temperature) for the safety population. The protocol-specified comparisons among treatment arms using ANCOVA will be limited to SBP and DBP (and not performed for pulse rate, respiration rate, and oral body temperature). Further, the resting SBP and DBP ANCOVA comparisons will be limited to the change from baseline to Day 14 (and not evaluated for the change from baseline to Days 7 or 28) since the effect would be more limited after only 7 days, and since subjects would have been off study drugs for 14 days at Day 28. The LOCF method of imputation will be applied for missing values.

**i. Orthostatic hypotension**

Descriptive statistics (n, mean, SD, median and range) will be added for the change from baseline at each visit (Days 7 and 14) for the orthostatic hypotension BP measurements (i.e., SBP and DBP after supine 5 minutes, standing 1 minute and standing 3 minutes, as well as the respective differences between standing and supine) for the safety population. The protocol-specified comparisons of the orthostatic hypotension BP measurements among treatment arms using ANCOVA will be limited to the change from baseline to Day 14 (and not evaluated for the change from baseline to Day 7) since any effect is anticipated to be maximal at Day 14. Further, the comparisons of the orthostatic hypotension diagnoses among treatment arms will be limited to Chi-square test or Fisher's exact test (and will not include logistic analyses as noted in the protocol) due to the limited number of subjects.

**j. Hematology, serum chemistry, and urinalysis**

For the majority of the hematology, serum chemistry, and urinalysis tests, the comparisons of the safety population data among treatment arms using Chi-square, binomial, and logistic analyses for dichotomous variables (e.g., negative/positive) and ANCOVA for continuous variables will not be done due to the limited number of subjects. The exceptions are serum creatinine and blood urea nitrogen (BUN), where comparisons between treatment arms will be performed using an ANCOVA model with change from baseline to Day 14 as the dependent variable, treatment as the fixed effect, and baseline as the covariate.

The laboratory reference range for assigning low "L" flags to the creatinine clearance results differed for the Celerion, Belfast laboratory (>90 mL/min) versus the centralized laboratory used for the remaining sites (ACM Global Central Laboratories;  $\geq 60$  mL/min). The serum chemistry shift table analysis will be based on the laboratory assigned flags (i.e., no reassignment of the Celerion, Belfast laboratory flags based on the ACM laboratory reference range will be made). The main body of the clinical study report will note the difference in the creatinine clearance reference range for the two

laboratories and will note by treatment group any cases where a Celerion, Belfast low creatinine clearance value would be reassigned as Normal if the  $\geq 60$  mL/min criterion was used.

Documentation of the differing creatinine clearance reference ranges for ACM and Celerion, Belfast is included in Appendix 16.1.10 of the clinical study report and in the individual subject laboratory reports that are included with the consolidated case report form PDF files, copies of which are included in the Trial Master File.

#### **k. Electrocardiogram (ECG)**

For analysis of ECG assessments, a shift table presenting the number and the percentage of subjects in each bivariate category (Initial Screening Visit versus Day 14) with regards to Investigator's interpretation (normal, abnormal NCS, abnormal CS, not done) by treatment arm will be done in place of a frequency only table. The protocol-specified comparisons among treatment arms using Chi-square, binomial, and logistic analyses will not be done since, based upon what is already known about amlodipine and celecoxib and what was demonstrated in the prior trial (KIT-302-03-01), minimal ECG effects are anticipated.

#### **1.3.10. BLQ computation for plasma concentration**

The protocol specifies that all plasma amlodipine concentration values below the lower limit of quantification (LLOQ) will be reported as zero. This will be modified as follows:

For the individual patient data listing of amlodipine plasma concentrations, all values below the LLOQ will be reported as below the limit of quantitation (BLQ), as in the bioanalytical report [Determination of Amlodipine in human plasma (lithium heparin) samples from "A Prospective Randomized Placebo Controlled Study to Evaluate the Effect of Celecoxib on the Efficacy and Safety of Amlodipine on Renal and Vascular Function in Subjects with Existing Hypertension Requiring Antihypertensive Therapy" by LC-MS/MS, bioanalytical report amendment number ACA20019 Am 1, Celerion Switzerland AG, March 22, 2018].

For the summary of non-transformed amlodipine plasma concentration values by treatment group by descriptive statistics (n, mean, SD, median, and range), as well as the t-test analysis of the non-transformed values and the box plot analysis of non-transformed values, all BLQ values will be treated as zero.

For the summary of log-transformed amlodipine plasma concentration values by treatment group by descriptive statistics (n, mean, SD, median, and range), as well as the t-test analysis of the log-transformed values, all BLQ values will be treated as 0.04 ng/mL rather than 0. Zero cannot be log-transformed. Assignment of the BLQ values to a nonzero number will allow computation of the log transformation. The selection of 0.04 ng/mL as the nonzero number for BLQ assignment was based on the LLOQ of the validated bioanalytical method [i.e., 0.05 ng/mL; Validation of an LC/MS/MS Method for the Determination of Amlodipine in Human Plasma (Li Heparin), method validation report number VZZ00140-01, MDS Pharma Services Switzerland AG, July 5, 2006; Validation of an LC-MS/MS Method for the Determination of Amlodipine in Human Plasma (Lithium Heparin), method validation report number VZZ46541, Celerion Switzerland AG, January 20, 2016] and selecting the next lowest number at the hundredth decimal place.

